**[name]**

**Advisor: [name] [name]**

**NCT Number: NCT05503680**

**Document date: January 7th, 20223**

## 1. Yoga protocol intervention

[figure not shown]
Participants in the yoga group engaged in eight biweekly online Hatha yoga classes for 120 minutes each at home. Classes began with 15 minutes of sitting meditation; breathing exercises; shoulder, neck, and back stretches; and sun salutations (either seated or standing). Following that, ten minutes of standing poses, fifteen minutes of balancing poses, and ten minutes of abdominal and back-bend positions will be performed. After 10 minutes of cool-down stretches and a final time of rest, all sessions was concluded. Physical postures and supportive props were modified to accommodate participants of all abilities. Participants was given an honorarium of Rp 50.000 or 3.49 USD at the baseline and final assessments. The full version of the yoga protocol is available in appendix III.

Table 3: Yoga protocol

Position	Main content	Length time
1. Warm-up	(1) Seated meditation, (2) Alternate (3) Nostril breathing, (4) Bellows breath, (5) Shoulder/neck stretches, (6) Cat-cow forward fold, (7) Sun salutations.	10 minutes
2. Standing poses	(1) Warrior one, (2) Warrior two, (3) Triangle, (4) Extended side angle, (5) Reverse warrior, (6) High lunge with twist.	10 minutes
3. Balance poses	(1) Tree pose, (2) Standing holding knee, (3) Modified warrior three (chair support), (4) Half-moon.	10 minutes

4. Abdominal and back bends	(1) Bird-dog, (2) Side plank, (3) Bridge, (4) Cobra, (5) Sphinx, (6) Baby position	10 minutes
5. Meditation	Full lotus, half lotus, Burmese	10 minutes
6. Cool down	(1) Twist, (2) Cobbler's pose, (2) Hip (3) Stretches, (4) Corpse pose, (5) Side-lying, (6) Seated on.	10 minutes

**All rights reserved**

## **Preface**

This 60-minute yoga protocol was developed for participants in the research project, "The effect of a yoga intervention for reducing stress among people living with HIV during the covid-19 pandemic in Indonesia, a randomized controlled trial."

You have been given a copy of this protocol because you are an HIV positive person and are undertaking a yoga intervention program to reduce stress. This protocol has an instructor and pictures of yoga poses to help you to practice yoga correctly. Share this protocol with your family, friends, or community who might need help to recover from stress related to HIV.

[name]

Doctoral student

February 3rd, 202

Position	Activity/purpose	Action plan		
Warm up (15 minutes)	
Activity:            (1) Seated meditation, (2) Alternate nostril breathing, (3) Bellows breath, (4) Shoulder/neck stretching, (5) Cat-cow forward fold, (6) Sun-salutation.
 
Maximum duration: 15 minutes
 
Purpose:
 
 
• Warming up for hatha yoga aims to help participants to prepare their minds to be centered, calm, and focused.
 
• A distracted mind prevents participants from reaping the deepest psychological and spiritual benefits from yoga practice.
 
 
Equipment:            Yoga mattress, chair, sport clothes, chair
	 1. Seated meditation	 2. Alternate nostril breathing	 3. Bellows breath

		
coming in and going out, letting thoughts float away like logs rolling down the river.
	
through the right side. Next inhale through your right nostril, then close it as you open the left nostril and exhale through the left side. This is one cycle. Repeat 5 times.
	
inhalation happening in between. Make sure the breath comes from your diaphragm, with your belly moving in and out. head, neck, shoulders, and chest

		 
4. Shoulder/neck stretching
	 
5. Cat-cow forward fold
	 
6. Sun salutation

		
Instruction: sit as in seated meditation. Place one of your hands behind your back with the other hand on top of your head. With the hand on your head, gently pull your ear toward your shoulder. Feel the stretch at the side of the neck. Hold it for 20 seconds and repeat three times. Then
	
Instruction: Begin on your hands and knees in the table pose, with your spine relaxed. As you exhale, come into cat pose by rounding your spine outward like a cat arching its back, tucking your tailbone in, and drawing your stomach in. Next, as you inhale, move into cow pose by lifting your sit bones
	
Instruction: Begin in a standing position with your feet slightly apart and parallel to each other, your palms turned out, and shoulders relaxed. Then follow this sequence of positions: mountain pose (i.e., standing with the palms of your hands facing towards your body alongside your thighs), Inhaling, lift both

repeat these steps for the other side.

upward, pressing your chest down and forward, lifting your head up and allowing your belly to sink. Relax your shoulders away from your ears, gazing straight ahead.

arms up. Exhaling, fold forward at the hips bringing your hands down to the mat. Step the right leg back and lunge. Then step the left leg back in plank, keeping body parallel to the floor. Then, bending your elbows bring the chest down to the ground. Push up with your hands, straightening the elbows and sliding forward into up dog. Curl the toes under, press down on feet and hands, lifting your hips up. Straighten elbows and knees. Then step your right foot forward so your right foot is parallel with your hands. Bring left foot up to the right foot and you are standing flexed at the hips in forward fold. Inhaling and standing up, swoop the arms out to the sides and above your head. Bring the palms together

				and lower them to your heart in namaste and back to mountain pose. The yoga instructor will demonstrate how to do this.
Standing pose (10 minutes)	
Activity: (1) Warrior one, (2) Warrior two, (3) Triangle, (4) Extended side angle, (5) Reverse warrior, (6) High lunge with twist.
 
Maximum duration: 10minutes
 
Purpose:
 
 
• Strengthen and stretch all muscle groups in the legs, particularly the thighs, hamstrings, buttocks, calves and ankles.
 
• Build balance and stability and improve flexibility.
 
• Reduce stress and promote better sleep.
 
	 
1. Warrior one
	 
2. Warrior two
	 
3. Triangle

degrees outward. Raise your arms straight above your head, keeping shoulders down. Squeeze your shoulder blades together and pull them downward. Lift your chin to gaze at your hands overhead. Hold this pose, then lower your arms and repeat on the left side.

knee until the knee is above your ankle. Extend your arms parallel to the ground. Relax your shoulders downwards. Turn your left foot out 90 degrees, then bend your right knee into a lunge. Be sure to keep the knee of your right leg above your ankle and pointing past your toes. Turn your head to the left and look beyond your fingers. Repeat this on the other side.

either on your left leg or touching the mat in the front of your left foot. Raise your right arm, extending it overhead and hold. Then repeat on the other side.

4. Extended side angle

5. Reverse warrior

6. High lunge with twist

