### **3. Statistical analysis plan**

Before performing statistical procedures, all data was entered into a computer and checked for errors. To analyze the data, the researcher then used SPSS computer software version 20. The data for all variables was manually coded before using the SPSS application, including demographic characteristics of patients, the perceived stress scale results brief health status survey, and coping self-efficacy. The alpha value was set at  $\alpha=0.05$  to determine the statistical significance of the variables. For demographic characteristics, the data analysis was descriptive statistics to identify the frequencies and percentages for categorical variables and the means and standard deviations for continuous variables. Before the statistical data processing begins, the data for independent and dependent variables was tested to determine its distribution and normality using plot histograms, logs and square roots, and checking residuals.

This study took repeated assessments over time and used a Generalized Estimating Equation (GEE) approach to model each study outcome and to predict the relationship of the variables while accounting for correlated data within the repeated measures (Hardin & Hilbe, 2007). The GEE technique, introduced by Liang and Zeger (1986), was the most often used strategy in marginal models, and it was a variation of Generalized Linear Modelling (GLM). GEE can handle correlated data with discrete, continuous, or binary outcomes. GEE is a non-likelihood or quasi-likelihood data modeling approach that specifies one of many working correlation matrix architectures to account for within-subject correlations (Liang & Zeger, 1986).

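### The yoga handout's preface gives HIV infection as the reason the holder has it and then asks the holder to share it, so sharing can reveal the holder's HIV status

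*Combined protocol and SAP*

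**What the plan says.** The Preface of the participant handout has four sentences.

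1. The first says that the handout was developed for participants in the research project and prints the project's title, which includes "reducing stress among people living with HIV during the covid-19 pandemic in Indonesia, a randomized controlled trial".
2. The second is addressed to the holder: "You have been given a copy of this protocol because you are an HIV positive person and are undertaking a yoga intervention program".
3. The third describes the content: "This protocol has an instructor and pictures of yoga poses to help you to practice yoga correctly".
4. The fourth is an instruction: "Share this protocol with your family, friends, or community who might need help to recover from stress related to HIV".

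The pose tables follow, from warm-up to cool-down. They give activities, durations, purposes and instructions. The available handout text has no separate version for sharing, no advice to detach the preface and no note that sharing may reveal something about the holder.

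**The concern.** The thing to be shared is the same document that gives HIV infection as the reason for having it. The instruction comes from the trial's own material and is worded as a plain imperative. It names broad groups (relatives, friends, community) and does not require that the recipient already knows the holder's status.

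What is at stake is participant protection, not inference. People were enrolled because of a confidential diagnosis. If the handout prompts them to disclose it unintentionally, the disclosure cannot be undone. Nothing in section 3, Statistical analysis plan, depends on this point.

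**Working it through.** No calculation applies, and the plan states no figure to reproduce. The check is a reading of the handout text.

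**Step 1: where HIV appears.** In the Preface, sentence 1 refers to it (title), sentence 2 does (the holder's status), sentence 3 does not, and sentence 4 does (the kind of stress). That is 3 of 4. In the pose tables, from warm-up to cool-down, there are 0 references. The count does not measure harm, since one sentence would be enough. It shows that the problem lies in the preface alone and that the poses can be taught without it.

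**Step 2: what a recipient could conclude.** Suppose the preface is passed on and read.

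- *The recipient takes* you *to mean the giver.* Sentence 2 then states the giver's HIV status outright.
- *The recipient takes* you *to mean themselves.* Sentence 2 then wrongly tells them that they are HIV positive and enrolled in the programme.
- *The recipient reads only the first sentence.* It links the handout to participants in a trial among people living with HIV. Someone who has a copy to give is plausibly such a participant.

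The first and third routes can reveal the giver's status. The second is a false statement about the recipient. No reading makes the page harmless to pass to someone who did not already know.

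**Step 3: whether a smaller edit would do.**

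| Only this is changed | What remains |
|---|---|
| Status sentence made neutral | The title still names the population, and the sharing sentence still mentions HIV |
| Title made neutral | Sentence 2 still states the holder's status |
| Sharing sentence deleted | The prompt is gone, but the page still states the status to anyone who sees it |

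All three sentences therefore need attention.

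**Step 4: what must be true for disclosure to occur.** The holder passes on the preface and not only the poses. The recipient reads it. The recipient connects it with the giver. The recipient did not already know. The documents give no information on how often these conditions hold together.

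**The case against.** The strongest reply is that the consequence is conditional. The visible text names no holder, sharing is at the holder's discretion, and the invitation is aimed at people affected by HIV-related stress, some of whom may already know. All of that stands. A reader might infer that every uninformed recipient learns the holder's status. The documents do not support this, because it assumes that every condition in step 4 is met. They support only that sharing *can* reveal it.

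A second reply is that participants may have been warned. The consent pages and some front matter just before the Preface are not in the available text. A caution there might be part of the handout itself, or might have reached the holder at consent, and the holder is the person who decides whether to share. A reader might infer that the trial gave no privacy safeguard, but that cannot be determined. What remains is that the preface, as worded, tells the holder to share, so any such caution would be working against the handout's own instruction.

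A third inference is that sharing contaminated the control arm and shrank the treatment difference. The available text does not describe the control arm, its contact with yoga participants or any yoga practice among controls. The written sun-salutation sequence ("Then follow this sequence of positions: mountain pose") might suggest that the handout can be used alone, but that entry ends by leaving the demonstration to the instructor. There is no basis for a contamination claim.

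**Conclusion.** The point holds as a matter of participant confidentiality. The preface states the holder's HIV status, prints a title that names the trial population, and asks the holder to pass the document on. Following that instruction can disclose the diagnosis to a recipient who did not know it, or can tell a recipient wrongly that they have it.

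Confidence is high on the wording, which is explicit. How often disclosure followed is unknown: the number of recipients, what they already knew and any caution given to holders cannot be derived from the documents. The conclusion assumes only that the preface may be passed on and read as written. It affects no estimand, analysis or test. The change should be made because the possible harm is irreversible and the remedy is nearly free.

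**What to change.** - Replace the status sentence with neutral wording, for example: *You have been given this guide because you are taking part in a yoga study.*
- Put a neutral study name in place of the full title in the first sentence.
- Delete the sharing sentence, or keep it without the reference to HIV.
- Use only this neutral version for any further circulation, and send it to people who already hold the current copy.

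The change is useful whether or not follow-up is complete. The largely past tense of sections 1 and 3 suggests that classes have been given, but the sharing instruction has no end date and copies may remain with participants.

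The cost is three reworded preface sentences and one re-sending to current holders. The pose pages stay as they are, and the statistical analysis plan needs no change.

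### The yoga booklet asks participants to pass it on to relatives, friends and community with no time limit; controls could receive it, an avoidable risk of modest dilution

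*Combined protocol and SAP*

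**What the plan says.** The booklet's Preface tells the reader: "You have been given a copy of this protocol because you are an HIV positive person and are undertaking a yoga intervention program". It explains the purpose of the material: "This protocol has an instructor and pictures of yoga poses to help you to practice yoga correctly". It then gives the instruction at issue: "Share this protocol with your family, friends, or community who might need help to recover from stress related to HIV". No start date, embargo or exception for other trial participants is attached.

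The same Preface describes the study as one of yoga for "reducing stress among people living with HIV during the covid-19 pandemic in Indonesia, a randomized controlled trial". A comparison group therefore exists, and its members are also people living with HIV.

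Section 1 (Yoga protocol intervention) says the classes were online and taken at home, and mentions a baseline and a final assessment. Section 3 (Statistical analysis plan) describes repeated assessments and says the study "used a Generalized Estimating Equation (GEE) approach to model each study outcome". On the data collected it says: "The data for all variables was manually coded before using the SPSS application, including demographic characteristics of patients", and goes on to name perceived stress, brief health status and coping self-efficacy. Yoga practice and receipt of the booklet by controls are not named, but the list is introduced as a set of examples and may be incomplete.

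**The concern.** The people the booklet is to be shared with overlap with the population from which controls come. The booklet sets out the poses step by step, so someone who receives it could practise at home. If controls did so before the final assessment, their mean would move toward the yoga mean. The randomised difference would be biased toward no effect and power would fall.

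The bias runs in one direction. Dilution cannot create a false benefit, so a positive result is not undermined. What is at stake is some loss of sensitivity, which matters most when the result is close to the significance threshold. The trial's own booklet prompts the exposure, so the risk is avoidable.

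**Working it through.** The available text gives no sample size, planned power, effect size, standard deviation or allocation ratio, so there is no figure of the plan's to reproduce. The calculation below only gives a sense of scale.

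**Inputs**
- Alpha = 0.05, from section 3. Sidedness is not stated; two-sided is assumed, so z = 1.960.
- Planned power of 80% is assumed, so z = 0.842.
- c = share of controls who practise from the booklet before the final assessment. Assumed 5%, 10% or 20%.
- f = fraction of the full yoga effect those controls obtain. Assumed one quarter or one half. A value well below 1 is reasonable because a booklet is a weaker exposure than a class: for the sun salutation, the booklet itself says "The yoga instructor will demonstrate how to do this".

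**Formulas**
- Observed difference = (1 − c·f) × true difference.
- Power = Φ((1 − c·f)(1.960 + 0.842) − 1.960) = Φ((1 − c·f) × 2.802 − 1.960).

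This is a normal approximation for a single comparison of two means with unchanged variance. It does not model the GEE analysis.

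**Results**

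| f | c | 1 − c·f | Shrinkage | Power |
|---|---|---|---|---|
| 0.25 | 5% | 0.9875 | 1.25% | 0.790 |
| 0.25 | 10% | 0.975 | 2.5% | 0.780 |
| 0.25 | 20% | 0.95 | 5% | 0.759 |
| 0.50 | 5% | 0.975 | 2.5% | 0.780 |
| 0.50 | 10% | 0.95 | 5% | 0.759 |
| 0.50 | 20% | 0.90 | 10% | 0.713 |

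Worked line for the last row: c·f = 0.20 × 0.50 = 0.10; 0.90 × 2.802 = 2.522; 2.522 − 1.960 = 0.562; Φ(0.562) = 0.713. Restoring 80% power in that row would need 1/0.90² = 1.23 times the sample size.

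**Could dilution of this size produce a null?** In the worst row the observed difference is still 90% of the true one. Halving the difference would need c·f = 0.5, for example half of all controls gaining the full effect or every control gaining half of it.

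**The case against.** The strongest reply is that every link to actual bias is undocumented. A yoga participant would have to know a control and pass on the booklet before the final assessment, and that control would have to practise enough to change a stress score. The text gives no recruitment sites, no social links between the arms and no hand-out date; the Preface's present tense is the only hint of timing. Classes were online and at home, so they brought the arms into no physical contact.

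The silence on safeguards is also weak evidence. Some pages were removed from the copy available for review, and what remains does not describe the control condition, recruitment or the instructions given to controls. A safeguard could exist elsewhere.

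All of that stands. It makes contamination a risk and not a demonstrated fault. It does not remove the instruction, which is in the text, has no time limit and was written by the trial itself.

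A reader might go further and infer that a null or small result could never be told apart from dilution. The documents do not support that. Shrinkage of 1.25% to 10% can move a borderline result but leaves nearly all of a worthwhile effect in place. Much steeper losses, such as power of about 61% or 50%, need 20% or 30% of controls to gain the full effect from a booklet, and nothing in the text suggests this.

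**Conclusion.** The point holds as an avoidable contamination risk. The sharing instruction is certain, and its possible overlap with the control arm follows from the trial's own population. That any control received or used the booklet is not shown.

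The direction would be toward no effect. The size cannot be estimated from the documents. Under the assumptions listed with the calculation, the loss is modest: at most a 10% smaller difference and a fall in power from 80% to about 71%. It could matter for a borderline result and would not by itself account for a null one. The change is worth making because it is nearly free.

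**What to change.** **If the trial is still running**
- In the booklet used during the trial, replace the sharing sentence with: *Please do not share this booklet until all participants in the study have completed the final assessment.* Offer the booklet to controls and the community after that.
- At the final assessment, after the outcome questionnaires so that the answers cannot influence them, ask both arms how often they practised yoga, and ask controls whether they received the booklet.
- Report the answers by arm beside the as-randomised GEE analysis, which stays unchanged. Do not exclude exposed controls.

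**If follow-up is complete**, as the mostly past tense of sections 1 and 3 suggests, report the sharing instruction, and any lack of data on control exposure, as a limitation that could have diluted the difference somewhat.

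**Cost.** In a running trial: one booklet sentence, two short questions, and a delay in community sharing until the last final assessment. In a completed trial: one sentence in the report.

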**Instruction:**  
Start in warrior two pose and reach your left arm up. Then, extend your left arm up above your ear, turning your thumb up and your pinky down. Continue to plant your feet firmly on the mat as you reach up. Then lean back slightly to gently twist your chest and core open. Press your right knee open toward your little toe. As you reach over your ear, keep abdominal muscles active and extend your spine, reaching your

**Instruction:**  
Start in warrior two, lift your right arm up to the ceiling. At the same time lower your left hand and slide it down your left leg. Move your shoulder blades together and pull your lower ribs in, lifting your chest as you come into a gentle backbend. Look at your raised hand. Stay in the pose for up to 5 breaths.

